9.4 Language and Hearing Assessments

The CELF-4 is a standardized test to be administered to those participants previously enrolled in AMP and who have completed at least one previous CELF-4 while in AMP. Only those participants in AMP who had at least one CELF completed in AMP will be administered the CELF-4 in AMP Up. The CELF-4 should be administered at the Entry visit for those participants who will be 22 years or older by the time of their Year 3 visit. All others will have the CELF-4 administered at the Year 3 visit. Clinical site staff can obtain a list of PIDs for participants that meet the criteria for CELF administration from the AMP Up CELF-4 Visit Calculator located on the Frontier Science PHACS Portal. The CELF-4 will be administered by centrally trained PHACS staff and does not require administration by a psychologist. Subtests include Recalling Sentences, Formulated Sentences, Word Classes-Receptive, Word Classes-Expressive, and Word Definitions. The assessment incorporates culturally appropriate contexts and visual stimuli. Updated norms are based on a diverse standardization sample of 2,650 participants that reflect the updated 2000 U.S. Census, including children with identified conditions and diagnosed language disorders (Semel et al., 2003). The Core Language and Expressive Language composite scores will be analyzed.

Participants will be screened at the Entry, Year 3, 6, 9, and 12 visits for hearing problems using the WIN hearing test from the NIH Toolbox. WIN measures a person's ability to recognize single words presented amid varying levels of background noise to assess how much difficulty a person might have hearing in a noisy environment. A recorded voice instructs the participant to listen to and then repeat words. The task becomes increasingly difficult as the background noise gets louder. See Section 9.3 for more information about the NIH Toolbox.

9.5 Blood Pressure

Systolic and diastolic blood pressure will be performed and recorded two times at each in-person visit using an appropriately-sized cuff. If the results differ by more than 5 mm Hg, a third reading should be obtained and all readings recorded.

9.6 Blood Tests

Refer to the schedule of evaluations in Appendices I and II for laboratory tests to be performed as part of this study.

The type of tube/anticoagulant for specific tests is critically important and testing specifications can be found in the AMP Up Laboratory Processing Chart (LPC).

See Section 9.8 and Appendix III for specimen collection specifications for repository specimens.

9.7 Fasting

Fasting is required for some specimens, unless determined to be unfeasible due to a valid medical condition by the local clinical investigator. The minimum duration of fasting is 8 hours. Water and medications are allowed during fasting.

9.8 Central Testing and Repository Specimens

Site personnel will be responsible for ensuring that the specimens for testing at the Central Laboratory and for storage in the PHACS Repository are appropriately collected and processed for storage.

- In the case of fasting serum and fasting plasma specimens, the serum and plasma must be separated within 24 hours of the draw. Blood for viable PBMCs/plasma should be collected and processed as soon as possible.
- For female participants, a vaginal swab will be self-collected by the participant for research Aptima STI testing at the Central Laboratory and two additional swabs will be collected for long-term storage at the PHACS Repository.
- About 20 ml of clean-catch urine will be collected after the first void of the day and processed and stored at the local lab until shipping to the PHACS Repository. The urine will be split into one 10-ml aliquot and two 5-ml aliquots for research Aptima STI testing, renal biomarker testing, and storage in the PHACS Repository, respectively.
- Unstimulated saliva (about 3 ml) will be collected using a sterile container and stored at the local lab until shipping to the PHACS Repository.
- About 10 ml but no less than 5 ml of throat wash/gargle will be collected, processed, and stored at the local lab until shipping to the PHACS Repository.

Shipping of repository specimens will occur on a regularly scheduled basis. See Appendix III of this protocol and the AMP Up LPC for detailed repository specimen collection and processing specifications.

9.9 STI Testing and Reproductive Health

Real-time screening for STIs (*N. gonorrhoeae*, *C. trachomatis*, and *T. vaginalis*) will be done annually for participants with neither *N. gonorrhoeae* nor *C. trachomatis* testing results available in the medical records from the 12 months prior to the visit. Results for both tests must be available in the record in order for the site to forego real-time STI testing. Self-collected urine for males and a self-collected vaginal swab for females will be tested for *N. gonorrhoeae*, *C. trachomatis*, and *T. vaginalis* at a local clinical lab and results made available to the site. It is preferred that testing be done on a vaginal swab for females because the swab is more sensitive than urine for the detection for cervical *N. gonorrhoeae*, *C. trachomatis*. However, if a female participant does not agree to vaginal swabs, urine should be collected. Participants will be instructed at the Entry visit by clinical site staff on the correct technique for specimen self-collection. The vaginal swab will be collected blindly and should not be inserted beyond the cervical os. When collection is required during years without in-person visits (e.g., Years 1, 2, 4, 5, 7, 8, 10, 11, 13, 14...), sites will provide participants with collection kits, instructions for collection and return of the sample to the clinical site, and a contact number in case of questions. The collection kit used will be determined by the testing requirements of the local laboratory. Collection kits will be provided discreetly, with no study name or description included on the packaging in order to protect the participant's confidentiality. If self-collection takes place at home, the specimen will be delivered or mailed by the participant to the clinical site, with the mode of delivery based on the requirements of the assay used by

the local laboratory. Most labs “test” for *T. vaginalis* in female participants by microscopic examination of a wet mount of vaginal secretions. Diagnosis of trichomoniasis in male participants is generally performed only when symptomatic by microscopic examination of urine. If the lab does not perform a specific test for *T. vaginalis*, wet mounts of vaginal secretions or urine are adequate. If real-time testing for *T. vaginalis* is not available or cannot be done for a participant, it should be considered missed and the reason it was not done should be documented in the participant’s research record.

Research Aptima STI research testing will also be conducted annually. Urine for males and a vaginal swab (preferred), or urine if swab is declined for females, will be self-collected by the participant at the clinic or at home and delivered to the clinical site. Similar to the real-time testing described above, it is preferred that testing be done on a vaginal swab for females. However, if a female participant does not consent to vaginal swabs, urine should be collected. The clinical site will then ship the samples to the PHACS Repository, where they will subsequently be forwarded in batches to the Central Laboratory for research Aptima STI testing for *N. gonorrhoeae*, *C. trachomatis*, *T. vaginalis*, and HPV (on vaginal swabs only). Clinical sites will be provided with the collection kits and shipping materials so the samples can be collected appropriately and delivered to the clinical site if the sample is self-collected at home. The Central Laboratory may not be a Clinical Laboratory Improvement Amendments (CLIA)-certified laboratory, so these results are for research purposes only. As stipulated in the consent, sites will be informed of positive results so that the participant can have repeat testing performed in a CLIA-certified or similarly approved clinical laboratory.

When the results of screening tests or examinations are ascertained through medical record review (urine, swab, genital visual exam, speculum aided exam, or blood), a copy of cervical cytology/histology and/or STI testing results will be obtained. If the participant has an abnormal cytology and is referred to colposcopy, a record of the histology results will also be obtained. It is expected that the diagnoses of atypical squamous cells of undetermined significance (ASCUS), LSIL, or HSIL will be made according to the Bethesda system for cervical cytological diagnosis by a laboratory at the location institution that is accredited by the Colleges of American Pathology.

The type of STI test (swab, urine, blood) and the date and result of the test (positive or negative) obtained from medical charts will be recorded. The results of clinical examinations done as part of routine care will be abstracted for AMP Up annually.

Participants in the YAPHEU cohort will be offered HIV testing at the Years 3 and 9 visits.

10.0 ADVERSE EVENT REPORTING

This study is not a therapeutic study and no medications are being prescribed as part of this study. Participants enrolled in this study may develop common conditions requiring treatment during the course of the study period. Study personnel will assist the participants in receiving appropriate care as appropriate to their roles at their sites. The participants may also experience adverse events associated with HIV infection, ART exposure, or other medications. Clinical site principal investigators are encouraged to use the FDA’s MedWatch system to report any events possibly associated with medications clinically prescribed for the participant. No adverse events associated with involvement in the study are anticipated.

11.0 STUDY IMPACT AND SAFETY MONITORING

Monitoring the full impact of research studies includes evaluating the impact of the study on the welfare of three groups of people:

- Research participants;
- Research staff; and
- The community in which the research is being conducted.

Reporting of participant or staff-associated negative study impact events to the Protocol Team will result in the examination of study procedures, as necessary, to address concerns about participant management, recruitment, enrollment, adequacy of training, and/or to modify procedures. Community-associated untoward event reporting will facilitate understanding of the impact of the study on the community and will provide the opportunity to address community-level concerns and to intervene in a timely manner to correct misinformation or perceptions of practices that may cause community concern.

All clinical sites have psychologists, social workers, or other staff qualified to address situations if a participant becomes distressed. In addition, PHACS has developed standard operating procedures for sites to follow in these circumstances (available on the PHACS website at <https://my.phacsstudy.org>).

11.1 Reporting Requirements

All more than minimal impact events involving study participants or staff are to be reported to the Protocol Team through the QNS by the clinical site. Any event that is deemed to have negatively impacted a participant to a more than minimal extent and is related to the study activity must also be reported to the PHACS Regulatory and Compliance Manager by the clinical site through the QNS. Reportable events could involve study participants and/or staff members.

Examples of more than minimal impact events for study participants that could be related to the study activity include:

- Disruptive or violent behavior during the scheduled study visit session;
- Information regarding personal harm which is disclosed or uncovered during interview or sessions (e.g., current suicidal or homicidal ideation, physical or sexual abuse, depression);
- Significant visible distress or injury resulting from the research encounter (e.g., responding to questions/surveys about exposure to violence, abuse, etc. may provoke emotional responses/distress and may require involvement of clinical staff to provide support/guidance to the participant); and
- Breach of confidentiality.

The PHACS Regulatory and Compliance Manager will be responsible for reporting such events to the HLC IRB. The PHACS Regulatory and Compliance Manager will also work with the site to ensure that the site's local IRB is notified of the event, as required.

Note: The distinguishing feature of more than minimal impact events is the need for enlisting additional support outside the research staff and the research encounter. The web-based surveys will include information on how and where participants can obtain assistance should they have feelings of anxiety, depression, suicidal ideation, etc. after completing the survey.

11.1.1 State Mandated Reporting Requirements

Laws governing the reporting of certain communicable diseases and illegal behaviors to authorities vary from state to state. Study sites are responsible for adhering to the reporting laws in their respective states. Study sites will consult with the HLC IRB and their local IRBs for guidance, when needed.

11.2 Monitoring Plan

NICHD has determined that a formal Data and Safety Monitoring Board will not be established; the NIH PHACS Management Oversight Committee (PMOC) will act as the oversight body for the study. The PMOC is comprised of program officials from NICHD, each co-funding NIH institute, and the NIH Office of AIDS Research (OAR).

12.0 ANALYTIC CONSIDERATIONS

The AMP study design initially included a PHIV cohort of 451 participants and a comparison cohort of 227 PHEU participants. Over the course of the AMP study, some youth were lost to follow-up, died, moved, or were otherwise unable to be continued in follow-up. Thus, the target sample size for the current AMP Up protocol has been expanded to targets of 650 YAPHIV and 200 YAPHEU enrolled at age 18 or older. The YAPHEU comparison cohort is expected to consist mostly of young adults exposed to ARVs *in utero*, but young adults unexposed to ARVs will not be excluded, just as they are not excluded from the YAPHIV group. Ideally, the comparison cohort will come from the same population as the YAPHIV group for comparability on many non-HIV measures that also influence outcomes of interest. Prenatal ART exposures in both groups will exhibit a time-confounding effect because of changes in clinical practice which cannot be controlled.

Evaluation of several stated study hypotheses will involve comparison of the distributions of outcomes between YAPHIV and YAPHEU. These comparisons will allow us to assess whether the outcomes are different between YAPHIV and YAPHEU. For some hypotheses, for example growth, neurocognitive measures, and HPV prevalence, the YAPHEU cohort will provide a comparison group from a similar socioeconomic background and home environment. However, there is little ability to separate out the effects of HIV infection from postnatal ART exposure due to the study design. It should be noted that many of our primary hypotheses for evaluating the impact of ART regimens on outcomes in this study will be evaluated by comparing assessments across subgroups of YAPHIV; these analyses will not include the YAPHEU cohort.

Since all participants previously enrolled in AMP Up from AMP are expected (when available) to have previous data collected from Women and Infants Transmission Study (WITS), Pediatric AIDS Clinical Trial Group (PACTG) 219C or a comparable cohort providing detailed ART exposure information, most of the statistical analyses described below will use the existing historical data from these studies in evaluating the hypotheses of this study. New AMP Up young adults who enroll but were not previously in AMP will have information on ART exposure abstracted from past data or completed by sites as necessary.

12.1 Power and Sample Size Consideration

In the context of this study, many targeted outcomes, some continuous (e.g., BMI, and height and weight z-scores) and some binary (insulin sensitivity, and neurodevelopmental impairment) will be measured.

For relatively rare events, the calculations for binary outcomes can serve as good approximations for survival outcomes, and for more common outcomes they often serve as an upper bound (i.e., a survival analysis would have greater power than comparison of proportions of events at a fixed time). All of the following calculations were conducted using PASS 15.0.4 (NCSS, 2017).

12.1.1 Comparisons between YAPHIV and YAPHEU

For continuous outcomes, the sample size of 650 YAPHIV vs. 200 YAPHEU provides 80% power to detect a difference in means of 0.227 standard deviations based on a 2-sample t-test (assuming normality holds), and 0.240 based on a non-parametric Wilcoxon rank sum test (for skewed outcomes) at alpha = 0.05. For example, if the full-scale IQ scores of YAPHIV is compared with YAPHEU and a standard deviation of 15 points is assumed, a difference of 3.40 points or more in the mean IQs could be detected. Assuming loss to follow-up and/or incomplete/missing assessments of 4% per year for infected and 6% per year for uninfected participants at two years after enrollment into AMP Up is completed, then an adjusted sample size of 415 YAPHIV vs. 101 YAPHEU provides 80% power to detect a difference of 0.311 standard deviations, or 4.67 points in mean IQ scores. Once adjusted for potential confounders, some power will typically be lost so the minimum detectable difference will usually increase.

For binary outcomes, the table below shows the minimum difference that can be detected in proportions in terms of the Odds Ratio (OR) based on comparing YAPHIV vs. YAPHEU, at 80% power with a 0.05 significance level. For this type of outcome, the detectable differences depend on the underlying rate of the event in the comparison cohort. For simplicity here, it is assumed that the event rate is higher in the YAPHIV cohort than the YAPHEU cohort.

Table 12.1. Minimum detectable ORs between YAPHIV and YAPHEU at 80% power and a 0.05 significance level for various event rates in the comparison cohort

Sample Size for YAPHIV Cohort	Sample Size for YAPHEU Cohort	Event rate in YAPHEU Cohort	Minimum Detectable OR	Detectable Rate in YAPHIV Cohort
650	200	4%	2.92	10.8%
		5%	2.64	12.2%
		10%	2.05	18.6%
		20%	1.73	30.2%
		30%	1.63	41.0%
415	101	4%	4.36	15.4%
		5%	3.79	16.6%
		10%	2.68	22.9%
		20%	2.13	34.7%
		30%	1.95	45.5%

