- Congenital and acquired CMV infection results in HIV disease progression and potentiates end-organ disease.
- Specific host genetic polymorphisms and epigenetic changes are associated with HIV disease progression, response to ART, response to co-infections, and specific end-organ disease.
- Chronic immune activation, lack of viral suppression, decreased CD4 counts, and ARV exposures will be independently associated with HIV disease progression and end-organ diseases.
- YAPHIV who are virally suppressed will have a higher incidence of end-organ disease than YAPHEU, related to immune activation.
- The viral dynamics, reservoir size, and compartmentalization of PHIV and the host response to the infection will be different than that of young adults without PHIV.
- Incident infections, including SARS-CoV-2, STIs, CMV, toxoplasmosis, and EBV, and the resulting immune activation, will lead to HIV disease progression and potentiate end-organ disease.
- Vaccine hesitancy will be less common among YAPHIV than YAPHEU.
- YAPHIV when compared to YAPHEU will be at increased risk of periodontal disease, resulting in local and systemic immune activation and alterations in the oral microbiome, which in turn will hasten the decline in oral health.
- Bone loss in YAPHIV will be associated with ARVs and immune activation.
- Both knowledge and use of PrEP by YAPHEU will be low; HIV infection will be uncommon.
- Use of PrEP will increase over time, but use of PrEP and its rate of change over time will vary by sex.

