12.2.5 Reproductive Health

The analysis of reproductive health outcomes will focus on estimating the prevalence and incidence of pregnancies (intended and unintended); pregnancy outcomes (live birth, induced abortion, spontaneous abortion, fetal death); the prevalence and incidence of menstrual irregularities; and the incidence of perinatal HIV transmission.

We will calculate prevalence estimates based on those with the specific outcome of interest divided by those with measurements for that outcome, along with 95% CIs. Incidence estimates will be calculated under a Poisson distribution based on participant-years of follow-up.

The prevalence of each outcome will be compared between the YAPHIV and the YAPHEU comparison group using chi-square tests as crude analyses and using logistic regression models for each separate outcome as a function of HIV status controlling for important demographic, and clinical and social factors (including but not limited to socioeconomic factors, partner characteristics, viral load, adherence, depression, and other behaviors).

Factors associated with prevalence of each outcome will be identified using logistic regression models. Factors associated with the incidence of each outcome will be identified using Cox-proportional hazards models. Factors associated with changes in reproductive health measures over time will be identified using GEE models, or mixed effect models when possible, to account for correlation between assessments on the same participant.

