12.2.8 Risk and Protective Behaviors

The analysis of behaviors will focus on estimating the prevalence at study entry and over follow-up of vaginal and anal sexual intercourse, condomless vaginal or anal intercourse, multiple sexual partners, substance use, recreational and medical marijuana use, and tobacco and alcohol use. The frequency of disclosure of HIV status to sexual partners, and of serosorting (asking about partner's HIV status) will also be evaluated. Prevalence estimates based on those with the specific outcome of interest divided by those with measurements for that outcome along with 95% CIs will be calculated. Incidence estimates will be calculated under a Poisson distribution based on participant-years of follow-up.

The prevalence of behaviors will be compared between the YAPHIV and the YAPHEU comparison group using chi-square tests as crude analyses and using logistic regression models for each separate outcome as a function of HIV status controlling for important demographic, clinical, and social factors (socioeconomic factors, partner characteristics, viral load, adherence, and perceived social support).

Factors associated with prevalence of risk factors will be identified using logistic regression models. Factors associated with the incidence of risk behaviors including condomless vaginal or anal intercourse and substance use will be identified using Cox-proportional hazards models. Factors associated with changes in risk behaviors over time will be identified using GEE models.

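### Table 12.1's 80%-power label is inaccurate in the 4%, 5% and 10% rows: actual unadjusted power at the printed odds ratios is about 85-94%, so those minimum detectable ORs are too large

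*Protocol*

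**What the plan says.** Section 12.1.1 of the protocol gives the detectable differences for binary outcomes between the two cohorts "at 80% power with a 0.05 significance level". Table 12.1 lists an OR and the matching YAPHIV rate for YAPHEU event rates of 4%, 5%, 10%, 20% and 30%. It does so for the full cohorts (650 and 200) and for the cohorts after losses (415 and 101). The table is titled "Minimum detectable ORs between YAPHIV and YAPHEU at 80% power and a 0.05 significance level for various event rates in the comparison cohort".

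The section does not name the test or formula behind the table. Section 12.1 names only the software, and adds that for relatively rare events the binary calculations can stand in for survival outcomes. The companion Table 12.3 in section 12.1.2 is attributed to logistic regression models.

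The analyses planned for these contrasts appear in the domain sections. Section 12.2.8 has prevalences "compared between the YAPHIV and the YAPHEU comparison group using chi-square tests as crude analyses", and section 12.2.5 likewise plans comparisons "using chi-square tests as crude analyses and using logistic regression models for each separate outcome as a function of HIV status". On direction, section 12.1.1 says that "it is assumed that the event rate is higher in the YAPHIV cohort than the YAPHEU cohort".

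**The concern.** A minimum detectable OR at 80% power should be the OR at which the planned test rejects 80% of the time. Large-sample formulas for the log odds ratio work poorly when one cell has a small expected count. In the 4-10% rows the expected YAPHEU events are 8, 10 and 20 (200 × 0.04, 0.05, 0.10), or about 4, 5 and 10 (101 × the same rates).

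Table 12.1 is the protocol's only quantified statement of what binary YAPHIV-YAPHEU contrasts can detect. Section 12.1 relies on the binary calculations for rare events in particular, which are the rows where the approximation is weakest. If those rows are off, a reader planning an analysis of an uncommon outcome is told that the cohort cannot reliably detect differences that it can.

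**Working it through.** **Inputs.** Sample sizes, YAPHEU event rates and printed ORs are from Table 12.1. Alpha is 0.05. Sidedness is not stated for the table; two-sided is assumed, and it reproduces the printed values. Write p2 for the YAPHEU rate, p1 = OR·p2/(1 − p2 + OR·p2) for the YAPHIV rate, and q = 1 − p.

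**Step 1: reproduce the table.** Formula: power = Φ(ln OR / SE − 1.96), with SE² = 1/(n1·p1·q1) + 1/(n2·p2·q2).

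Example, 415 vs. 101 at 4%: OR 4.36 gives p1 = 0.1537. Then SE = √[1/(415 × 0.1537 × 0.8463) + 1/(101 × 0.04 × 0.96)] = 0.526, ln 4.36 / 0.526 = 2.80, and power = Φ(0.84) = 80.0%.

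Solving for 80% in every row gives:
- 650 vs. 200: 2.918, 2.635, 2.051, 1.733, 1.627 (printed 2.92, 2.64, 2.05, 1.73, 1.63).
- 415 vs. 101: 4.361, 3.786, 2.678, 2.126, 1.950 (printed 4.36, 3.79, 2.68, 2.13, 1.95).

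All ten match to rounding. The 50:50 rows of Table 12.3 also reproduce from this formula to within 0.01. Pooled, unpooled, continuity-corrected and arcsine formulas, and a one-sided test, do not reproduce the rare-event rows.

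**Step 2: actual power at the printed ORs.** For every pair of counts (x, y) with X ~ Bin(n1, p1) and Y ~ Bin(n2, p2), apply the test at two-sided 0.05 and sum the probabilities of the rejecting pairs.

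| n1 / n2 | YAPHEU rate | Printed OR | Formula | Pearson chi-square | Logistic Wald |
|---|---|---|---|---|---|
| 650/200 | 4% | 2.92 | 80% | 89.4% | 89.2% |
| 650/200 | 5% | 2.64 | 80% | 88.2% | 88.2% |
| 650/200 | 10% | 2.05 | 80% | 85.1% | 84.6% |
| 415/101 | 4% | 4.36 | 80% | 94.2% | 91.8% |
| 415/101 | 5% | 3.79 | 80% | 92.5% | 91.3% |
| 415/101 | 10% | 2.68 | 80% | 87.7% | 87.3% |

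In the 20% and 30% rows both tests give 82-84%. Chi-square size under the null is 0.045-0.050 in every row and Wald size is below 0.05, so the extra power does not come from an inflated type I error.

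**Step 3: why the formula misses.** It fixes the SE at the expected YAPHEU count. The decision is made at larger counts, where the SE is smaller. Take 415 vs. 101 at 4%, with 64 YAPHIV events (415 × 0.1537 ≈ 63.8) and about 4 expected YAPHEU events:
- y = 7: ln[(64/351)/(7/94)] = 0.895; SE = √(1/64 + 1/351 + 1/7 + 1/94) = 0.415; ratio 2.16, reject.
- y = 8: ln[(64/351)/(8/93)] = 0.751; SE = √(1/64 + 1/351 + 1/8 + 1/93) = 0.393; ratio 1.91, do not reject.

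At the boundary the SE is about 0.40, not 0.526.

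**Step 4: ORs that do give 80% power, with the YAPHIV rate in brackets.**

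| n1 / n2 | YAPHEU rate | Printed | Pearson chi-square | Logistic Wald |
|---|---|---|---|---|
| 650/200 | 4% | 2.92 (10.8%) | 2.63 (9.9%) | 2.65 (9.9%) |
| 650/200 | 5% | 2.64 (12.2%) | 2.43 (11.3%) | 2.43 (11.3%) |
| 650/200 | 10% | 2.05 (18.6%) | 1.97 (18.0%) | 1.98 (18.0%) |
| 415/101 | 4% | 4.36 (15.4%) | 3.52 (12.8%) | 3.69 (13.3%) |
| 415/101 | 5% | 3.79 (16.6%) | 3.19 (14.4%) | 3.27 (14.7%) |
| 415/101 | 10% | 2.68 (22.9%) | 2.47 (21.5%) | 2.49 (21.7%) |

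**The case against.** The strongest defence is that nothing was miscalculated. A standard formula was applied consistently, it belongs to one of the planned analyses, and it returns 80% in every row. That stands against calling this an arithmetic slip. It does not rescue the label, because the logistic Wald test that the formula approximates itself has about 85-92% power at those ORs.

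The defence also says that the gap is conservative, that it is small at 20-30%, and that section 12.0 sets the 650 and 200 targets without reference to this table. All of that stands, and it limits the severity.

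A third objection is that the replacement ORs depend on the test. This also stands. With a Yates correction, which the protocol neither specifies nor excludes, the 80%-power ORs in the 4-10% rows are 2.74, 2.51, 2.02 and 3.79, 3.41, 2.58. Even so, Yates power at the printed ORs there is 82-91%, so no candidate test gives 80%.

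Finally, smaller crude ORs could look optimistic for adjusted models. Section 12.1.1 warns, after its continuous-outcome results, that adjustment usually raises the detectable difference. The corrected table should carry the same warning.

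A reader might go further and say that the table misleads on hypotheses predicting fewer events in YAPHIV, such as "Vaccine hesitancy will be less common among YAPHIV than YAPHEU" in section 2.2.1, because inverting the ORs would overstate power. The documents do not support calling that an error: the one-direction assumption is stated openly, and nothing invites the reader to take reciprocals.

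**Conclusion.** The point holds in limited form. In the 4%, 5% and 10% rows of Table 12.1, the printed ORs carry about 85-89% unadjusted power (650 vs. 200) or 87-94% (415 vs. 101), not 80%, for Pearson chi-square and logistic Wald. The stated minimum detectable ORs are therefore too large. The worst row is 4% with 415 vs. 101, where a printed 4.36 should be roughly 3.5 to 3.7. The 20-30% rows need no correction of substance.

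This rests on a two-sided 0.05 test, independent binomial counts at the tabled sizes, no covariate adjustment, and a higher event rate in YAPHIV as the section assumes.

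A reader might infer that the study is mis-sized or its power overstated. Neither follows: in the tabulated direction the table understates power, and no sample size derives from it. Severity is low.

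**What to change.** Name the test behind Table 12.1 and recompute the 4%, 5% and 10% rows for it by exact enumeration. For uncorrected Pearson chi-square the ORs are about 2.63, 2.43 and 1.97 (650 vs. 200) and 3.52, 3.19 and 2.47 (415 vs. 101). For logistic Wald they are about 2.65, 2.43 and 1.98, and 3.69, 3.27 and 2.49. Update the detectable-rate column to match. Add a sentence saying that the figures are unadjusted and that covariate adjustment will usually raise them. A panel for lower rates in YAPHIV would be useful but is optional.

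The cost is one rerun table and a line or two of protocol text. Enrolment, data collection and the planned analyses are untouched.
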